12.3 Statistical Analyses	
13 REGISTRATION GUIDELINES	
14 DATA SUBMISSION SCHEDULE	27
15 SPECIAL INSTRUCTIONS	27

15.1	Patient-reported questionnaires	27
15.2	Correlative Studies	
16 ETHI	CAL AND REGULATORY CONSIDERATIONS	29
16.1	Informed consent	29
16.2	Human Subjects Protections	29
16.3	Institutional Review	
16.4	Data and Safety Monitoring Plan	29
16.5	ADVERSE EVENTS	30
16.5.1	Experimental Therapy	30
16.5.3	Definitions	31
16.5.4	Adverse Event Characteristics	33
16.5.7	Reporting of Unanticipated Problems	34
16.6	Reporting of Pregnancy	34
16.7	Protocol Amendments	35
16.8	Protocol Deviations	
16.9	Food and Drug Administration (FDA)	35
16.10	Clinical Trials Data Bank	35
17 REFE	ERENCES	35

ABBREVIATIONS

[figure not shown]
AI	Aromatase inhibitor
AIMSS	Aromatase inhibitor-associated musculoskeletal symptoms
BPI	Brief Pain Inventory
CBD	Cannabidiol
CNS	Central nervous system
DSMC	Data and Safety Monitoring Committee
ER	Estrogen receptor
GRC	Global Ratings of Change
HR	Hormone receptor
IRB	Institutional Review Board
LHRH	Luteinizing Hormone Receptor Hormone
METE	Mao Expectation of Treatment Efficacy
NSAID	Non-steroidal anti-inflammatory drugs
O-CTSU	Oncology Clinical Trial Support Unit
PANAS	Positive and Negative Affect Scale
PARP	Poly adenosine diphosphate-ribose polymerase
PR	Progesterone receptor
SAE	Serious adverse event
THC	Δ^9 -tetrahydrocannabinol

T'41-	Dhage 2 Trial of Connehidial (CDD) for		
Title	Phase 2 Trial of Cannabidiol (CBD) for Treatment of Aromatase Inhibitor-Associated		
	Arthralgias		
Short Title	CBD for AIMSS (CBD-AIM)		
Protocol Identifiers (IRB – internal)	HUM00182109		
IND number	TBD		
Phase	Phase 2		
Design	Single arm phase II interventional trial		
Study Duration	2.5 years		
Study Center(s)	Single-center		
Objectives	Primary Objective:		
	To determine the effect of 15 weeks of CBD on AI-associated worst joint pain, as assessed with the Brief Pain Inventory (BPI)		
	Secondary Objectives:		
	To determine the effect of 15 weeks of CBD on other AI-associated pain symptoms, including average pain and pain interference, as assessed with the BPI		
	To determine the effect of 15 weeks of CBD on other AI-associated symptoms, including anxiety, depression, insomnia, and cognitive function, as assessed with the PROMIS-29+2 Profile		
	To examine the safety and tolerability of 15 weeks of CBD in patients with breast cancer taking aromatase inhibitor therapy		
	To examine the effect of 15 weeks of CBD on circulating estradiol concentrations		
	Exploratory objectives:		
	To examine the impact of 15 weeks of CBD therapy on inflammatory biomarkers in patients with breast cancer taking aromatase inhibitor therapy		

STUDY SUMMARY

	To examine demographic, clinical, psychosocial, and inflammatory predictors of response to CBD therapy
Number of Subjects	44 (goal 40 evaluable patients)
Study drug	Cannabidiol 25 mg – 100 mg BID orally
Duration of administration	15 weeks
Reference therapy	N/A
Statistical Methodology	The primary endpoint of this study is the absolute difference in worst pain from baseline to 15 weeks with CBD. Differences from baseline at each time point for all patient reported outcomes (worst and average pain severity, pain interference, sleep disturbance, fatigue, physical function, anxiety, depression, and cognitive function over time) will be summarized via mean, standard deviation, and the change in the pattern over time will be explored with linear mixed models including a subject-specific random effect to account for the natural heterogeneity across patients. Normalizing transformations will be used if necessary to ensure accurate model fit. Secondarily, the proportion of patients who have at least a 2-point reduction in worst and average pain from baseline to 15 weeks will be reported with the corresponding exact binomial confidence intervals.

SCHEMA

1 OBJECTIVES

1.1 Primary Objective

To determine the effect of 15 weeks of CBD on AI-associated worst joint pain, as assessed with the Brief Pain Inventory (BPI)

1.2 Secondary Objectives

- 1. To determine the effect of 15 weeks of CBD on other AI-associated pain symptoms, including average pain and pain interference, as assessed with the BPI
- To determine the effect of 15 weeks of CBD on other AI-associated symptoms, including anxiety, depression, insomnia, and cognitive function, as assessed with the PROMIS-29+2 Profile
- 3. To examine the safety and tolerability of 15 weeks of CBD in patients with breast cancer taking aromatase inhibitor therapy
- 4. To examine the effect of 15 weeks of CBD on circulating estrogen concentrations

1.3 Exploratory Objectives

- 1. To examine the impact of 15 weeks of CBD therapy on inflammatory biomarkers in patients with breast cancer taking aromatase inhibitor therapy
- 2. To examine demographic, clinical, psychosocial, and inflammatory predictors of response to CBD therapy

2 BACKGROUND

- 2.1 Hypothesis
- 2.2 Rationale and Background:

Aromatase inhibitor (AI) therapy for breast cancer

Breast cancer is the most common cancer diagnosis among women in the United States, affecting one in eight women in her lifetime. With advancements in screening and treatment, nearly 90% of women diagnosed with breast cancer in the United States (US) survive beyond five years and comprise an estimated 25% of cancer survivors. About 80% of breast cancers diagnosed in postmenopausal women are hormone receptor

positive (HR+). For these women, daily oral adjuvant endocrine therapy for five to ten years following primary treatment (surgery, radiation, chemotherapy) is indicated.¹

Third generation AIs are the preferred endocrine treatment for postmenopausal women with early stage HR+ breast cancer. Aromatase is the key enzyme that converts androgens to estrogens. In postmenopausal women, aromatase is only expressed in non-glandular tissues including fat, liver, brain, and breast tissues.² AIs prevent the biosynthesis of estrogen in these tissues, thus preventing the proliferation of HR+ breast cancer cells. Large-scale comparative effectiveness trials demonstrated the superiority of AIs over other endocrine treatment (i.e., tamoxifen), in terms of prolonged disease-free survival, rates of distant metastasis, and contralateral breast cancer, as well as a preferable toxicity profile.³

AI-Associated Musculoskeletal Symptoms (AIMSS)

Despite their clinical utility, AIMSS affect ~50% of the 200,000 patients who start AI therapy per year in the US.⁴ Musculoskeletal symptoms, including arthralgias, myalgias, and joint stiffness, are the primary symptoms reported by AI-treated patients. These symptoms typically emerge within about 3 months of AI initiation, and peak at 6 months.^{4, 5} Despite considerable research, the etiology of AIMSS remains poorly understood.^{4, 6-9} Postulated mechanisms include inflammation and reductions in naturally anti-nociceptive properties of estrogen.^{10, 11} While multiple randomized clinical trials of AIMSS treatments have been conducted, only a few interventions including acupuncture and duloxetine have demonstrated improvement in musculoskeletal pain and stiffness,^{12, 13} and are currently unavailable to most patients due to access issues (acupuncture) and perceived stigma and toxicity (duloxetine).

AIMSS can lead to early treatment discontinuation in one-fifth of patients, which can increase risk of breast cancer recurrence by 45-50%.^{4, 14-16} Despite well-established clinical benefits of long-term AI treatment, more than 20% of patients discontinue AI therapy prematurely, primarily because of toxicity of therapy. While the primary toxicity of therapy is AIMSS, AI-treated women also report bothersome vasomotor and gynecologic symptoms, as well as insomnia, fatigue, anxiety, and depression. In addition, studies have shown an increase in inflammatory markers in patients with co-existing symptoms, supporting an underlying inflammatory mechanism.¹¹ Discontinuation of AI therapy before the recommended 5-10 years has been shown to increase risk of cancer recurrence and mortality.¹⁴⁻¹⁶ Therefore, well-tolerated and effective interventions to improve AI-associated symptoms, primarily AIMSS, are urgently needed.

Cannabinoids

Cannabinoids produce analgesia in patients with pain.¹⁷ These compounds, such as cannabidiol (CBD) and Δ^9 -tetrahydrocannabinol (THC), act on cannabinoid receptors 1 and 2 (CB1 and CB2) and other receptors in the endocannabinoid system, which are involved in complex behaviors and responses such as pain, sleep, and mood.¹⁸⁻²⁰ THC's activation of CB1 receptors is primarily responsible for the psychoactive effects that characterize cannabis intoxication.^{21, 22} In contrast to THC, CBD is non-intoxicating

and well tolerated in numerous medical conditions. CBD-related adverse events are minor, even in the context of long-term, high-dose paradigms.²³⁻²⁸ CBD is a promiscuous compound that acts on numerous systems (e.g., the serotonergic 5HT1a receptor, transient receptor potential cation channel subfamily V member 1) and exerts anti-inflammatory and analgesic effects.²⁸ In a recent clinical trial among individuals with chronic pain due to knee osteoarthritis, transdermally-administered CBD significantly reduced pain and improved function.²⁹ Murine models of induced arthritis provide mechanistic support for this finding, as CBD slowed arthritis progression, prevented and/or reduced joint damage, and reduced spontaneous tumor necrosis factor release following lipopolysaccharide injection.^{26, 27} Further, CBD administration during days 0-3 of monoiodoacetate-induced arthritis in a rat model dramatically reduced tactile allodynia and inhibited nerve demyelination, suggesting that early CBD administration could protect against nerve damage from inflammatory flares.²⁸

CBD also exerts anxiolytic effects, which is of special import given that anxiety is common among individuals with breast cancer and is associated with worsened pain symptoms.³⁰⁻³² A recent clinical trial among individuals with social anxiety disorders showed that 300mg of CBD/day for 4 weeks resulted in decreased anxiety. Acute CBD administration (300-600 mg) has been shown to decrease anxiety compared to placebo during public speaking tasks.³³⁻³⁶ In a retrospective chart review among 47 psychiatric outpatients, CBD (25-175 mg/day) reduced anxiety scores by 31% after 3 months.³⁷ Taken together, these anti-inflammatory, analgesic, and anxiolytic effects suggest that CBD may have value as an analgesic in AIMSS. Although CBD is widely used by the general public for pain, arthritis, and anxiety, clinical research on CBD is limited and no clinical trials have examined CBD alone for cancer pain. Thus, the proposed study will shed light on precisely how CBD is exerting its analgesic effects in patients with AIMSS, as well as rigorously investigate the safety profile in this condition.

Cannabidiol

Until recently, the only options for conducting clinical trials of CBD was to use overthe-counter products, which are highly variable in potency, there is poor quality control and testing for contaminants (e.g., heavy metals), and products are typically not consistent from lot to lot due to inherent variability in the hemp crop. However, a prescription version of CBD (Epidiolex) was recently FDA approved for treatment of refractory seizures in children. This formulation is ideal for testing in patients with AIMSS because it is non-intoxicating, is produced using Good Manufacturing Practices, which guarantee consistent product quality, and is not illegal under federal law.

Cannabidiol is relatively well tolerated at higher doses than planned in this trial; doses for treatment of refractory seizures are typically 5-20 mg/kg/day. Doses planned in this trial are 25 mg BID to 100 mg BID. For a 50 kg person, this is equivalent to a range of 1-4 mg/kg/day. For an 80 kg person, this is equivalent to a range of 0.625-2.5 mg/kg/day.

Assessment of AIMSS

No published scales have been established or validated to specifically measure the effects of treatments for AI-induced joint pain and stiffness. Therefore, we have chosen to use a combination of scales to assess the effect of CBD for improving tolerance of AI therapy. As has been used in multiple prior trials of treatments for AIMSS, patients will complete self-reported questionnaires including the Brief Pain Inventory-Short Form (BPI-SF)³⁸ to assess severity of joint pain/stiffness and the Global Ratings of Change (GRC) scale to identify overall change in pain/stiffness since starting AI therapy. To assess other symptoms related to endocrine therapy, patients will complete the PROMIS-29+2.³⁹ To assess expectation of benefit from CBD, patients will complete multiple questionnaires to further characterize pain and associated psychosocial symptoms, including the 2011 Fibromyalgia Survey to assess symptoms, the PANAS to assess affect, and a coping questionnaire to assess catastrophizing. All of these questionnaires are described in greater detail in section 10.

3 DRUG INFORMATION

3.1 Cannabidiol

3.1.1 Pharmacology

The mechanism of action of CBD for treatment of pain is not entirely clear. CBD has weak affinity for CB1 and CB2, but binds to other receptors, including serotonin 5-HT_{1A}.^{41, 42} CBD is well tolerated in humans at doses up to 700 mg/day^{43, 44} and is non-intoxicating.⁴⁵ In animal studies, CBD exerts anti-inflammatory and anti-nociceptive effects, and slows arthritis progression.²⁶⁻²⁸ However, no systematic mechanistic studies of CBD have been conducted in individuals with chronic pain.

3.1.2 Physical and Chemical Properties

Cannabidiol is a cannabinoid designated chemically as 2-[(1R,6R)-3-Methyl-6-(1-methylethenyl)-2-cyclohexen-1-yl]-5-pentyl-1,3-benzenediol (IUPAC/CAS). Its empirical formula is C₂₁H₃₀O₂ and its molecular weight is 314.46. Cannabidiol, the active ingredient in EPIDIOLEX, is a cannabinoid that naturally occurs in the*Cannabis sativa L*. plant. Cannabidiol is a white to pale yellow crystalline solid. It is insoluble in water and is soluble in organic solvents.

3.1.3 Pharmaceutical Properties and Formulation

EPIDIOLEX (cannabidiol) oral solution is a clear, colorless to yellow liquid containing cannabidiol at a concentration of 100 mg/mL. Inactive ingredients include dehydrated alcohol, sesame seed oil, strawberry flavor, and sucralose. EPIDIOLEX contains no ingredient made from a gluten-containing grain (wheat, barley, or rye).

3.1.4. Pharmacokinetics

Cannabidiol demonstrated an increase in exposure that was less than dose-proportional over the range of 5 to 20 mg/kg/day in patients.

Absorption

Cannabidiol has a time to maximum plasma concentration (Tmax) of 2.5 to 5 hours at steady state (Css).

Effect of Food

Co-administration of EPIDIOLEX with a high-fat/high-calorie meal increased Cmax by 5-fold, AUC by 4-fold, and reduced the total variability, compared with the fasted state in healthy volunteers.

Effect on P-glycoprotein (P-gp) substrates

Coadministration of EPIDIOLEX with orally administered everolimus, a P-gp and CYP3A4 substrate, results in an approximately 2.5-fold increase in mean Cmax and AUC of everolimus *[see Clinical Pharmacology (12.3) in the drug prescribing information]*. When initiating EPIDIOLEX in patients taking everolimus, monitor therapeutic drug levels of everolimus and adjust the dosage accordingly. When initiating everolimus in patients taking a stable dosage of EPIDIOLEX, a lower starting dose of everolimus is recommended, with therapeutic drug monitoring. Increases in exposure of other orally administered P-gp substrates (e.g., sirolimus, tacrolimus, digoxin) may be observed on coadministration with EPIDIOLEX. Therapeutic drug monitoring and dose reduction of other P-gp substrates should be considered when given orally and concurrently with EPIDIOLEX.

Distribution

The apparent volume of distribution in healthy volunteers was 20963 L to 42849 L. Protein binding of the cannabidiol and its metabolites was >94% in vitro.

Elimination

The half-life of cannabidiol in plasma was 56 to 61 hours after twice-daily dosing for 7 days in healthy volunteers. The plasma clearance of cannabidiol following a single EPIDIOLEX 1500 mg dose (1.1 times the maximum recommended daily dosage) is 1111 L/h.

Metabolism

Cannabidiol is metabolized in the liver and the gut (primarily in the liver) by CYP2C19 and CYP3A4 enzymes, and UGT1A7, UGT1A9, and UGT2B7 isoforms. After repeat dosing, the active metabolite of cannabidiol, 7-OH-CBD, has a 38% lower AUC than the parent drug. The 7-OH-CBD metabolite is converted to 7-COOH-CBD, which has an approximately 40 fold higher AUC than the parent drug. Based on preclinical models of seizure, the 7-OH-CBD metabolite is active; however, the 7-COOH-CBD metabolite is not active.

Excretion

EPIDIOLEX is excreted in feces, with minor renal clearance.

3.1.4 Clinical Safety

Cannabidiol had the following adverse reactions in clinical trials of EPIDIOLEX (%):
--

Adverse reaction	CBD 10	CBD 20	Placebo
	mg/kg/day	mg/kg/day	
Elevated transaminases	8	16	3
Decreased appetite	16	22	5
Diarrhea	9	20	9
Decreased weight	3	5	1
Gastroenteritis	0	4	1
Abdominal pain	3	3	1
Somnolence	23	25	8
Sedation	3	6	1
Lethargy	4	8	2
Fatigue	11	12	4
Insomnia	11	5	4
Irritability	9	5	2
Aggression	3	5	<1
Salivary hypersecretion	1	4	<1
Gait disturbance	3	2	<1
Infection	41	40	31
Rash	7	13	3
Нурохіа	3	3	1

Adverse reactions were similar across pediatric and adult patients.

Epidiolex can cause decreases in hemoglobin. The mean decrease in clinical trials was 0.42 g/dL, compared to a decrease of 0.03 g/dL on placebo.

Epidiolex can cause increases in serum creatinine; the mechanism is unknown. An increase of approximately 10% was observed within 2 weeks of starting Epidiolex. The increase was reversible in healthy adults.

4 STUDY DESIGN

4.1 Description

This will be a single arm phase 2 trial of CBD to examine the safety and efficacy of 15 weeks of CBD in postmenopausal women with AIMSS. In addition, change in inflammatory biomarkers with treatment will be examined to obtain preliminary information about the mechanism of action of CBD in this condition, and to identify predictors of response to therapy.

4.2 Number of Patients

A total of 44 patients will be enrolled, assuming a 10% dropout rate, for a total of 40 evaluable patients. Patients who discontinue trial participation prior to initiating CBD therapy will be replaced.

4.3 Number of Study Centers

This will be a single center trial run at the Rogel Cancer Center at the University of Michigan.

4.4 Study Duration

The study is anticipated to be open for 2.5 years.

5 ELIGIBILITY CRITERIA

5.1 Inclusion Criteria Yes/No (Response of "no" = patient ineligible)

- **5.1.1** Female subject aged ≥ 18 years who is postmenopausal according to standard clinical criteria (see section 8.3) or who has been receiving concomitant LHRH agonist therapy.
- **5.1.2** Taking the currently prescribed aromatase inhibitor therapy (anastrozole, exemestane, or letrozole) for adjuvant treatment of breast cancer or for chemoprevention for at least 3 weeks and no more than 2 years at the time of enrollment.
- **5.1.3** Planning to take the same AI therapy for at least 15 weeks.
- **5.1.4** New or worsening joint pain and/or myalgias since starting the AI therapy, with *worst* pain score of at least 4 out of 10 on the BPI over the 7 days prior to enrollment.
- **5.1.5** Completion of surgery (mastectomy or lumpectomy/partial mastectomy) for treatment of breast cancer at least 3 months prior to enrollment. Completion of axillary surgery as indicated (not required).
- **5.1.6** Completion of chemotherapy, if given. Concurrent use of LHRHa therapy, anti-HER2 therapy, bisphosphonate therapy, PARP inhibitor therapy, and CDK4/6 inhibitor therapy is permitted.
- **5.1.7** Patients receiving treatment with NSAIDs, acetaminophen, opioids, duloxetine, gabapentin, and/or pregabalin must have been taking a stable dose for at least 30 days prior to enrollment if they plan to continue the drug during study participation. If they do not plan to take the medication during study participation, they should stop the medication at least 7 days before initiation of study treatment.
- **5.1.8** _____ ECOG Performance Status 0-2.
- **5.1.9** Able to self-complete questionnaires in English.
- **5.1.10** Able to provide informed consent and willing to sign an approved consent form that conforms to federal and institutional guidelines.

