9 STUDY CALENDAR

Required Studies	Screening ª	Baseline ^b	Weeks 1, 2, 3 (+/- 2 days) ^c	Weeks 4, 6 (+/- 2 days) ^c	Week 8 (-2, +7 days) ^c	Week 12 (+/- 2 days) ^c	Week 15 (-2, +7 days) ^{c, j}	Off Study (if prior to week 15) ^d
Informed consent	Х							
Medical History	Х							
Performance status ^m	Х							
Study visits ⁱ	Xd	Х			Х		Х	Х
Study coordinator phone calls ^{k, n}			Х	Х	Х	X	XI	XI
Vital signs ^e	Х							
Concomitant medications	Х	Х						
Adverse event assessment			Х		Х		Х	Х
Patient reported questionnaires ^f								
- BPI	Х	Х	Х	Х	Х	Х	Х	Х
- PROMIS		Х		X (wk 4 only)	Х		Х	Х
- GRC			X°	X (wk 4 only)	Х	Х	Х	Х
- METE		Х						
- FM Survey		Х					Х	Х
- CSQ		Х					Х	Х
- PANAS		Х					Х	Х
- PHQ9 ^p	Х	Х						
Phlebotomy ^g								
- Research	X ^r X				X X		Х	X X
 Clinical labs (aspartate aminotransferase, alanine aminotransferase, total 	X			X (wk 4 only)	Х		X	X
bilirubin, serum creatinine, complete blood count)								
Al therapy (standard of care)								•
Dispense study medicine		Х			Х			
CBD treatment ^h								
Medication log		Х			Х		Xi	Xi

a. Screening and baseline visits can take place on the same day. The informed consent can be completed either in person or remotely using SignNow. The BPI and PHQ9 will be completed after signing the ICF and can be completed by phone or electronically. Screening clinical lab studies must be completed within 28 days of registration; if they have already been completed for another reason (other than participating in this clinical trial) they do not need to be repeated.

b. Baseline visit can take place up to 4 weeks after the screening visit. Patient does not need to be seen by physician or advanced practice provider.

c. Timed based on initiation of CBD therapy.

d. This is the visit conducted at the time of AI discontinuation and/or study drug discontinuation as per section 7.3.1. These questionnaires should be completed within 3 business days of medication discontinuation. Patients will return remaining study drug and medication log at that study visit or at their next routine clinic

visit. Also if a patient discontinues study drug early, she should continue to complete questionnaires according to the study calendar through the 15 week timepoint.

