e. Height and weight at screening visit. If these values have been documented in the medical record within 90 days they do not need to be repeated. f. Questionnaires will be completed electronically within 2 days before the scheduled visit, at the time of the visit, or within 2 days after the visit. It is preferable to have patients complete the questionnaires before or at each visit. Emailed reminders will be sent to patients from REDCap, and telephone reminders may also be used. If a scheduled visit is rescheduled after the questionnaires have been completed by the patient, they will not be considered out of window. If a patient declines to complete questionnaires electronically they may be completed on paper (baseline and week 8 and 15) or by phone (all timepoints).

g. It is preferred, but not required, that subjects fast for at least 8 hours prior to all blood collections (except for week 4). Time of blood draw and fasting status should be recorded. Details about research labs are in section 15.2.1.

h. Study medication should begin the first Wednesday morning after the baseline visit whenever possible. If the baseline visit is on a Wednesday, the participant can start the study medication the evening of the baseline visit. The medication should be taken with food twice a day approximately 12 hours apart.

i. At weeks 8 and 15 or off study, patient will meet with research study coordinator or otherwise return the medication log and/or remaining medication to the study team, depending on the timepoint. Patient does not need to be seen by physician or advanced practice provider. Patients will return medication log #1 at the 8 week study visit and return all remaining study drug and medication log #2 at the 15 week study visit, or at the off study visit if it occurs at a different time. If they forget to bring the medication and log to the visit, they should return the items at their next routine clinic visit.

j. For patients who wish to continue on therapy beyond the 15 week study visit, clinicians can provide a written prescription for off-label Epidiolex and/or provide recommendations for patients to go to local cannabis dispensaries in Michigan (since recreational cannabis is legal in this state), but drug will not be provided by the clinical trial following the week 15 study visit.

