10.2 Patient-Reported Outcomes

The validated instruments used in this study are as follows:

Brief Pain Inventory (BPI): The BPI is a 17-item patient self-rating scale that assesses sensory and reactive components of pain.³⁸ For sensory components, it addresses severity, location, chronicity, and degree of relief due to therapy. For reactive components, it assesses depression, suffering, and perceived availability of relief. Reliability has been demonstrated over short intervals using test retest item correlation; worst pain, r=0.93, usual pain, r=0.78, pain now r=0.59. It has been validated in patients with both cancer and non-cancer pain.^{46, 47} Ratings of pain interference with various activities increased as ratings of pain severity were higher. The proportion of patients receiving opioid analgesics also increased with increased severity rating.

The BPI uses 0 to 10 numeric rating scales for item rating because of its simplicity and lack of ambiguity. Since pain can be variable over a day, the BPI asks patients to rate their pain at the time of completing the questionnaire, and also at its worst, least, and average over the previous 7 days. The primary endpoint for this clinical trial will be based on the 7-day worst joint pain and/or myalgias as reported on the BPI. The ratings can be combined to give a composite index of pain severity. Also, using numeric 0 to 10 scales, with 0 being "no interference" and 10 being "interferes completely", the BPI asks for ratings of the degree to which pain interferes with mood, walking and other physical activity, works, social activity, relations with others, and sleep. The mean of these scores can be used as a pain interference score. This will be completed at each timepoint.

PROMIS-29+2 Profile v2.1: A validated questionnaire that assesses patient-reported symptoms over the past 7 days in 9 PROMIS domains (fatigue, sleep disturbance, physical functioning, depression, anxiety, ability to participate in social roles and activities, cognitive function-abilities, and pain intensity and interference). Raw scores for each domain are calculated and then converted to a T-score, with a mean of 50 and a standard deviation of 10. Higher T scores represent more of the concept being measured.³⁹ Pain severity and interference will be excluded since overlaps with BPI. This 26-item questionnaire will be completed at baseline, 4, 8, and 15 weeks (and off study if patient discontinues before week 15).

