12.3 Statistical Analyses

12.3.1 Primary endpoint

The primary endpoint is defined as the absolute change in BPI worst pain from baseline to 15 weeks. This change will be reported with the corresponding 95% confidence interval. Differences from baseline at each time point for worst pain will be summarized via mean and standard deviation. Patient reported outcomes will be analyzed using linear mixed effects models and include a subject-specific random effect to account for the natural heterogeneity across patients. Normalizing transformations will be used if necessary to ensure accurate model fit.

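### Section 5.1.7 times the analgesic stop from the first CBD dose, not from the 7-day-recall baseline BPI, so a compliant stopper's baseline score can cover days on the analgesic

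*Combined protocol and SAP*

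**What the plan says.** Section 5.1.7 of the combined protocol and SAP gives users of NSAIDs, acetaminophen, opioids, duloxetine, gabapentin or pregabalin two routes. They may continue on a dose that has been stable for 30 days before enrollment. If they do not plan to continue, "they should stop the medication at least 7 days before initiation of study treatment". The reference date for stopping is thus the first CBD dose.

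The endpoint uses a different date. Section 12.3.1 states: "The primary endpoint is defined as the absolute change in BPI worst pain from baseline to 15 weeks". Under section 10.2 the BPI rates current pain and "also at its worst, least, and average over the previous 7 days". The study calendar (section 9) places the baseline BPI at the baseline visit. Footnote f lets it be completed "within 2 days before the scheduled visit, at the time of the visit, or within 2 days after the visit" and adds: "It is preferable to have patients complete the questionnaires before or at each visit".

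Footnote h sets the start of CBD: "Study medication should begin the first Wednesday morning after the baseline visit whenever possible". For a Wednesday visit, "the participant can start the study medication the evening of the baseline visit", which is an option and not a requirement. Section 7.1.1 allows the drug to be mailed if the patient cannot attend the baseline visit.

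The outer limits are wide. Footnote a permits screening and baseline on the same day. Footnote b says: "Baseline visit can take place up to 4 weeks after the screening visit". Section 13 requires treatment to begin within 4 weeks of registration.

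Neither section 7.2.1, the calendar nor section 12.3 links the stop to the baseline BPI. Section 7.2.1 covers only women still taking these drugs when CBD starts.

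**The concern.** A washout before a change-from-baseline measure should clear the period that the baseline describes. Here it clears the week before the first dose, while the baseline describes the week before a questionnaire that is usually completed earlier.

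If the analgesic lowered pain in the recalled week and the woman is off it at week 15, her baseline is too low and her improvement is understated. The trial has a single arm, so no control group cancels the artefact. It enters the primary estimate directly. It can also affect the secondary responder proportion (a reduction of at least 2 points in worst pain), where one misclassified woman among 40 moves the result by 1/40 = 2.5 percentage points.

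The protocol uses an earlier reference date elsewhere. The 30-day stability rule in 5.1.7 and the 7-day valproate/clobazam stop in 5.2.7 both run from enrollment.

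**Working it through.** **Scale, from the plan's own figures (section 12.2).** The plan gives n = 40 evaluable, SD 3, two-sided 5%, and 80% power at effect size 0.45 or 1.4 points. A one-sample t-test on the change gives 79.3% power at 0.45 and 82.1% at 1.4/3 = 0.467, so the stated figure reproduces. With the same SD applied to the change, the 95% confidence interval half-width is t(0.975, 39) × 3/√40 = 2.02 × 0.474 ≈ 0.96 points.

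**Date arithmetic.** Let the first CBD dose be day 0. A stop at the permitted minimum means off the analgesic from day −7. A BPI completed g days before the first dose recalls the 7 days before completion. The on-analgesic days in that recall are min(g, 7), or 0 if g is 0 or negative. Here g = (days from visit to first dose) − (completion day relative to the visit). Weekday visits are assumed.

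| Visit | Days to first dose | On-drug days: BPI 2 days early | 1 day early | Visit day | 1 day late | 2 days late |
|---|---|---|---|---|---|---|
| Mon | 2 | 4 | 3 | 2 | 1 | 0 |
| Tue | 1 | 3 | 2 | 1 | 0 | 0 |
| Wed, same evening | 0 | 2 | 1 | 0 | 0 | 0 |
| Wed, next Wednesday | 7 | 7 | 7 | 7 | 6 | 5 |
| Thu | 6 | 7 | 7 | 6 | 5 | 4 |
| Fri | 5 | 7 | 6 | 5 | 4 | 3 |

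A recall that is wholly on-drug arises in three ways:

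- a Wednesday visit with a start the following Wednesday and the BPI on or before the visit day;
- early completion at a Thursday visit (1 or 2 days) or a Friday visit (2 days);
- a start delayed beyond these lags. For example, a woman who has screening and baseline on one day and stops that day cannot start CBD for at least 7 days. Her visit-day recall is then all on-drug although she has complied.

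**Size.** The documents give no share of stoppers, no analgesic effect and no distribution of visit or completion days. The assumptions are:

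- 0 to 20% of patients stop, all at the 7-day minimum;
- the analgesic effect is up to 2 points;
- visits are spread equally over the five weekdays, and completion days equally over the window;
- only wholly on-drug recalls count, because a worst-pain item behaves like a maximum and off-drug days in the window can set the score.

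Mean bias = share of stoppers × effect × fraction of schedules wholly on-drug. The maxima (20%, 2 points) are:

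| BPI completion | Wednesday visits start that evening | Wednesday visits start next Wednesday |
|---|---|---|
| Visit day only | 0/5: 0 | 1/5: 0.2 × 2 × 0.20 = 0.08 |
| 2 days before to 2 days after | 3/25: 0.2 × 2 × 0.12 = 0.048 | 6/25: 0.2 × 2 × 0.24 = 0.096 |
| 2 days before to visit day (preferred in footnote f) | 3/15: 0.2 × 2 × 0.20 = 0.08 | 6/15: 0.2 × 2 × 0.40 = 0.16 |

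Every minimum is 0, with no stoppers. Delayed starts are not counted and could raise these figures.

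**The case against.** **It is immaterial.** The largest figure above, 0.16 points, is about one sixth of the confidence interval half-width (0.16/0.96) and about 11% of the 1.4-point detectable change. It also assumes that everyone stops at the minimum, although the rule only sets a floor. This stands, and it is why the point is minor.

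**The favoured direction is conservative.** Understating improvement does not create a false positive. This mostly stands. Rebound pain after stopping could raise the baseline instead, and the understatement requires that the woman is still off the drug at week 15.

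**Registration may already protect the baseline.** Section 13 requires all section 5 criteria to be met before registration. If sites apply this so that stoppers have stopped by then, and registration precedes the BPI, a wholly on-drug recall cannot occur. The documents do not settle that sequence. A stop timed from the first dose need not have happened by registration, so section 13 does not close the gap.

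**Timing a washout from treatment start is defensible.** It keeps women with worst pain of at least 4 off analgesics for a shorter time. That is a real trade-off, and it is counted under the fix.

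**A stronger reading.** A reader might infer that the primary endpoint is seriously compromised. If 30% of patients stopped and each had a baseline 2 points too low, the bias would be 0.3 × 2 = 0.6 points, and power at a true 1.4-point change would fall to about 38%. The documents support neither input. That case also gives every stopper the full deficit, whereas many permitted schedules leave off-drug days in the recall that can set a worst-pain score.

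**Conclusion.** The gap is real on the text. A woman who complies fully with 5.1.7 can have between 0 and 7 on-analgesic days in the recall that defines her baseline. With a visit-day BPI the count is 2 for Monday, 1 for Tuesday, 0 or 7 for Wednesday, 6 for Thursday and 5 for Friday.

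It does not follow that every stopper is affected. Earlier stops, late completion after Monday or Tuesday visits, and a Wednesday visit with a visit-day BPI and evening start all avoid the overlap.

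Under the stated assumptions the mean bias is 0 to about 0.08 points if Wednesday visits start that evening, and up to about 0.16 points if they start the next Wednesday, with delayed starts uncounted. The likely direction is understated improvement, but this is not certain. The effect is probably small and does not threaten the trial. It is an optional improvement, worth making because it takes one sentence.

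**What to change.** Reword the last sentence of 5.1.7 along these lines: patients who will not continue the medication stop it at least 7 days before the baseline BPI is completed, and complete that BPI before the first CBD dose. On-analgesic recall days then become 0 for every schedule. The second clause is needed because a BPI completed 2 days after a Wednesday-evening start falls on day +2, which would otherwise allow a stop on day −5, later than the present rule permits.

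Costs:

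- The analgesic-free period before CBD for stoppers becomes 7 to 14 days with a visit-day BPI (lag of 0 to 7 days, plus 7). It reaches 16 days with completion 2 days early (7 + 2 + 7). Both fit the 4-week limits in footnote b and section 13.
- A woman who stops after consent can no longer use same-day screening and baseline. Her baseline becomes a separate later contact, possibly remote with mailed drug.
- A stop at exactly 7 days makes the recall the first drug-free week, so rebound pain could still enter. The present rule has the same limit for a Wednesday visit with a visit-day BPI and evening start.

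No questionnaire is added, and the sample size is unchanged.
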